# Protocol

# **Revision History**

Version Number (Date)	Summary of Revision(s)	Justification for Revision(s)
Version 1.0 (04 October	None – new document	Not applicable
2018)		
Version 2.0 (15 October	• Typographical edits	Administrative
2018)	• Update to Table 7 to include	Clarification on
	assignment of SPOT	intraoperative
	GRADE ™ score immediately	procedure
	prior to hemostat application	requirements
	
 
Addition of coordinating
 
	
	investigator [name]	

# 1 SYNOPSIS

Title	Prospective, Randomized, Controlled, Multicenter, Post-Market		
	Clinical Study Evaluating the Performance of HEMOBLAST ™		
	Bellows Compared to FLOSEAL Hemostatic Matrix in		
	Cardiothoracic Operations		
Protocol Number	ETC 2018-005		
Purpose/Objectives	To evaluate the performance (time to hemostasis, including device		
	preparation time) of HEMOBLAST ™ Bellows compared to		
	FLOSEAL Hemostatic Matrix		
Indication	HEMOBLASTTM Bellows is indicated for use in surgical		
	procedures as an adjunct to hemostasis when control of minimal,		
	mild, and moderate bleeding by conventional procedures is ineffective or impractical, except in neurosurgical, ophthalmic,		
	ineffective or impractical, except in neurosurgical, ophthalmic, and urological procedures.		
	and urological procedures.		
Study Design	Prospective, randomized, controlled, post-market		
Number of Subjects/Sites	A maximum of 104 subjects enrolled across a maximum of 5		
Proparativa Inclusion Critaria	A subject must meet all of the following pressperative inclusion		
rreoperative inclusion Criteria	criteria to be enrolled into the study:		
	Subject is undergoing a non-emergent cardiothoracic		
	surgery and		
	• Subject or an authorized legal representative is willing and		
	• Subject of an authorized legal representative is willing and able to give prior written informed consent for study		
	able to give prior written informed consent for study		
Preoperative Exclusion Criteria	A subject must not meet any of the following preoperative		
	exclusion criteria to be enrolled into the study:		
	• Subject has a known sensitivity or allergy to bovine and/or		
	porcine substance(s) or any other component(s) of the		
	hemostatic agent;		
	• Subject has religious or other objections to porcine or		
	bovine components; and		
	• Subject is not appropriate for inclusion in the clinical		
	study, per the medical opinion of the Principal		
	Investigator.		
Intraoperative Inclusion	A subject must meet all of the following intraoperative inclusion		
Criteria	criteria to be enrolled into the study:		
	• Subject in whom the Investigator is able to identify a		
	Target Bleeding Site (TBS) for which any applicable		
	conventional means for hemostasis are ineffective or		
	impractical; and		
	• Subject has a TBS with minimal, mild, or moderate		
Assossment Schedule	Dreenerstive		
Assessment Schedule	Preoperative     Obtain concent		
	• Obtain consent		
	• Confirm englolity criteria		
	Confirm eligibility criteria		
	Randomization		
	$\circ$ Performance evaluations		

	
 
Safety assessments
 
	
Test Device	HEMOBLAST ™ Bellows (Biom'up, France), hereinafter referred	
	to as HEMOBLAST ™	
Comparator Device	FLOSEAL Hemostatic Matrix (Baxter Healthcare Corporation,	
	Hayward, CA, USA), hereinafter referred to as FLOSEAL	
Primary Endpoint	The primary endpoint of this study is the superiority of	
	HEMOBLAST ™ relative to FLOSEAL for the proportion of	
	subjects reaching hemostasis within 3 minutes.	
Secondary Endpoints	The secondary endpoint of this study is non-inferiority of	
	HEMOBLAST ™ relative to FLOSEAL for the proportion of	
	subjects reaching hemostasis within 5 minutes.	

# **2 INTRODUCTION**

## 2.1 Purpose

The purpose of this study is to evaluate the performance of HEMOBLAST™ compared to FLOSEAL.

#### 2.2 Device Name

HEMOBLAST™ will be used in this study.

#### **2.3** Indication for Use

HEMOBLAST™ is indicated for use in surgical procedures as an adjunct of hemostasis when control of minimal, mild, and moderate bleeding by conventional procedures is ineffective or impractical, except in neurosurgical, ophthalmic, and urological procedures.

#### 2.4 Study Overview

#### 2.4.1 Duration of the Study

The estimated duration of the study is approximately 8 months from the time of first subject enrollment to the last subject enrollment. Enrollment occurs intraoperatively after confirmation of the intraoperative eligibility criteria. Subjects will undergo intraoperative performance assessments and then will be discontinued from the study after completion of the intraoperative visit.

## 2.4.2 Number of Subjects and Sites

A maximum of 104 subjects will be enrolled across a maximum of 5 study sites in the United States.

It is expected that approximately 20 subjects will be enrolled per site, with no more than 50% of the subjects being enrolled at any single site.

# **3 DEVICE DESCRIPTION**

## 3.1 Test Device Description and Indication for Use

HEMOBLAST™ consists of a powder composed of collagen, chondroitin sulfate, and thrombin. The powder is dry, sterilized, biocompatible, and non-pyrogenic. It is resorbed within 4 weeks. No preparation, mixing or heating is required.

HEMOBLAST™ is composed predominantly of highly purified porcine collagen with smaller amounts of bovine chondroitin sulfate and human pooled plasma derived thrombin. Each device contains a maximum of 1500 IU of thrombin. Plasma donations are from US plasma centers only. All individual donations of the plasma were tested for HBsAg, anti-HIV1/-HIV2, and anti-HCV and found to be negative. The plasma pools were tested and found to be non-reactive for HCV RNA, HBV DNA, and HIV1 RNA as determined by PCR (NAT). The product complies with the specifications of the manufacturer and World Health Organization (WHO).

The manufacturing procedures for HEMOBLAST™ include processing steps designed to reduce the risk of viral transmission.

HEMOBLASTTM is approved by the United States Food and Drug Administration (FDA) for use in surgical procedures as an adjunct to hemostasis when control of minimal, mild, and moderate bleeding by conventional procedures is ineffective or impractical, except in neurosurgical, ophthalmic, and urological procedures.

The Instructions for Use are included as Appendix A.

## **3.2** Test Device Manufacturer Details

The manufacturer of HEMOBLAST™ is Biom'up SA, which is located in Saint Priest, France. Biom'up is ISO 13485 certified.

## 3.3 Control Device

The control device for this study is FLOSEAL, which is distributed by Baxter Healthcare Corp. located in Hayward, California. The 5 mL Full Sterile Prep kit will be utilized for this clinical study.

# 4 BACKGROUND AND RATIONALE

## 4.1 Definition of Hemostasis

Despite advances in surgical techniques, excessive bleeding remains a major complication associated with surgery and contributes to poor clinical outcomes. There is no universally accepted definition of hemostasis. The most current definition is the "cessation of bleeding." The term comes from the Greek roots *heme* (blood) and *stasis* (halt). Hemostasis can be considered as control of bleeding within the finely tuned balance of procoagulant, anticoagulant, fibrinolytic, and anti-fibrinolytic activities.

Hemostasis refers to the process of causing blood to form a clot (the opposite of hemostasis is hemorrhage). Most of the time, this process includes the changing of blood from a fluid to a solid state.

Intact blood vessels are central to moderating blood's tendency to clot. The endothelial cells of intact vessels prevent blood coagulation by secretion of heparin-like molecules and thrombomodulin and prevent platelet aggregation by the secretion of nitric oxide and prostacyclin. When endothelial injury occurs, the endothelial cells cease secretion of coagulation and aggregation inhibitors and instead secret von Willebrand factor and tissue thromboplastin which initiates the maintenance of hemostasis after injury. Hemostasis has three major steps: vasoconstriction, formation of a platelet plug, and blood coagulation.

# 4.2 Current Hemostatic Therapeutic Strategies

Hemorrhage control is vital for successful clinical outcomes after surgery. It is essential to decrease postoperative morbidity and operative time, leading to potential cost savings.5, 6, 7 During surgical operations, it is important to maintain a fine balance between bleeding and clotting so that blood continues to flow to the tissues at the surgical site without excessive blood loss. There are many tools used for hemorrhage control; these include preventive measures, transfusion of blood products, and traditional methods.2

Conventional techniques for obtaining hemostasis during surgery include a variety of manual, mechanical, and thermal techniques. Application of direct pressure or compression at a bleeding site is often the surgeon's first choice to assist in the control of bleeding. The placement of direct pressure over the injury site serves to compress vascular structures and promote localized clotting. Direct pressure, while widely accepted as standard of care for the control of all levels of bleeding severity, has limited discourse in the surgical literature. Other mechanical methods, including sutures, staples, and ligating clips, are useful if the source of bleeding is easily identifiable and able to be sealed.

Compression and other mechanical methods may not be appropriate during all surgical procedures; this method of controlling bleeding may not be sufficient when the source of bleeding is hard to identify, as for diffuse venous bleeding. Moreover, the mechanical methods are not applicable in some surgical procedures because of localization and the inaccessibility of structures.

To summarize, conventional techniques show their limits in terms of bleeding control efficacy.7, 8, 9, 10, 11 Furthermore, they may be associated with the occurrence of complications.10

## 4.3 Rationale

Although the properties of the ideal local hemostatic agent may vary according to the surgical specialty, some properties are universally valued including: rapid and effective control/cessation of bleeding; ability to make effective contact with the bleeding surface; acceptable safety profile; and ease of preparation and use.

According to Spotnitz *et al.*, the ideal hemostat, sealant or adhesive must have certain performance characteristics (safety, efficacy, usability, cost, and approvability) that enable it to be used by surgeons. Biom'up has developed and manufactured a hemostatic device, HEMOBLASTTM, which is ready to use without any preparation required. This post-market study will be conducted to assess time to hemostasis, which includes the time of device preparation.

## 5 METHODOLOGY

## 5.1 Overall Study Design

This is a prospective, randomized, controlled, multicenter, post-market clinical study.

# 5.1.1 Objectives

The objective of this study is to evaluate the performance (time to hemostasis, including device preparation time) of HEMOBLASTTM compared to FLOSEAL.

# 5.2 Primary Efficacy Endpoint

The primary endpoint of this study is the superiority of HEMOBLAST™ relative to FLOSEAL for the proportion of subjects reaching hemostasis within 3 minutes.

## 5.3 Secondary Efficacy Endpoints

The secondary endpoint of this study is non-inferiority of HEMOBLAST™ relative to FLOSEAL for the proportion of subjects reaching hemostasis within 5 minutes.

## 5.4 Additional Exploratory Outcomes

The additional exploratory outcomes of this study include:

- Number of operating room interruptions during preparation of the hemostatic device;
- Proportion of HEMOBLAST™ vs. FLOSEAL subjects hemostatic at 3 minutes by baseline bleeding severity (minimal, mild, or moderate); and
- Proportion of HEMOBLAST™ vs. FLOSEAL subjects hemostatic at 5 minutes by baseline bleeding severity (minimal, mild, or moderate).

## 5.5 Subject Selection Criteria

A maximum of 104 subjects undergoing non-emergent cardiothoracic surgery will be enrolled into the clinical study. Subjects will need to meet all eligibility criteria to be enrolled into the study, as detailed below.

## 5.5.1.1 Preoperative Inclusion Criteria

A subject must meet all of the following preoperative inclusion criteria to be enrolled into the study:

- Subject is undergoing a non-emergent cardiothoracic surgery; and
- Subject or an authorized legal representative is willing and able to give prior written informed consent for study participation.

## 5.5.1.2 Preoperative Exclusion Criteria

A subject must not meet any of the following preoperative exclusion criteria to be enrolled into the study:

- Subject has a known sensitivity or allergy to bovine and/or porcine substance(s) or any other component(s) of the hemostatic agent;
- Subject has religious or other objections to porcine or bovine components; and
- Subject is not appropriate for inclusion in the clinical study, per the medical opinion of the Investigator.

## 5.5.1.3 Intraoperative Inclusion Criteria

A subject must meet all of the following intraoperative inclusion criteria to be enrolled into the study:

- Subject does not have an active or suspected infection at the surgical site;
- Subject in whom the Investigator is able to identify a Target Bleeding Site (TBS) for which any applicable conventional means for hemostasis are ineffective or impractical; and
- Subject has a TBS with minimal, mild, or moderate bleeding.1

Table 1.	Enrollment Based	on Surface Bleeding	g Severity Scale (	(SBSS)	/ SPOT GRADE TM Score
				()	

SBSS Score	0	1	2	3	4	5
Verbal Descriptor	None	Minimal	Mild	Moderate	Severe; not immediately life- threatening	Extreme; immediately life- threatening
Visual Descriptor	Dry	Oozing	Pooling	Flowing	Streaming	Gushing
Expected Intervention(s)	None	Manual pressure, cautery, adjuvant hemostat(s)	Manual pressure, cautery, suture, adjuvant hemostat(s)	Manual pressure, cautery, suture, adjuvant hemostat(s)	Manual pressure, cautery, suture, staples, tissue repair	Manual pressure, cautery, suture, staples, tissue repair
Maximum Expected ACS-ATLS Shock Risk Class Eligible for Enrollment	1 No	1 Yes	1 Yes	2 Yes	3 No	4 No

## 5.6 **Point of Enrollment**

All patients presenting to the Investigator for a non-emergent cardiothoracic operation are potential study subjects and should be screened for eligibility. Subjects will need to meet all eligibility to be enrolled into the study.

A subject is enrolled when he/she meets all preoperative inclusion/exclusion criteria, signs the informed consent form, and meets the intraoperative inclusion criteria. The point of enrollment into the clinical study will occur intraoperatively.

## 5.7 Withdrawal Criteria

Subjects may withdraw from the study at any time without providing a reason. Subjects will not be penalized nor lose any benefits to which they are otherwise entitled if they should choose to withdraw. The Investigator may also choose to withdraw the subject if he or she feels that this is in the subject's best interest.

Subjects who withdraw from the study before receiving the test or control hemostatic device will receive routine care. No study-specific assessments will be conducted.

#### 5.8 Subject Compliance

Subject loss to follow-up is not expected, as the endpoints are collected intraoperatively and there are no follow-up visits after the surgical procedure.

#### **6 STUDY PROCEDURES**

#### 6.1 Schedule Overview

Table 2 details the study visits, corresponding timing, and evaluations to be performed at the visit. Table 3 lists the Case Report Forms (CRFs) that need to be completed at each visit.

Visit	Timing	Evaluations
Preoperative	Prior to surgery	Informed consent, preoperative eligibility
		criteria confirmation
Intraoperative	Day of surgery	Intraoperative inclusion criteria confirmation,
_		enrollment and randomization, performance
		evaluation, and safety assessments

#### Table 2. Study Evaluation Schedule

# Table 3. CRF Completion Schedule

CRF	Preoperative	Intraoperative	Subject Study Completion
Preoperative CRF	X		
Intraoperative CRF		Χ	
Discontinuation CRF			X
Adverse Event CRF		0	
Device Deficiency CRF		0	

Χ	Mandatory
0	As applicable

## 6.2 **Preoperative Evaluations**

## 6.2.1 Informed Consent

Prior to performing any study specific procedures, a detailed explanation of the study procedures, potential discomforts, risks and benefits of participation, and alternatives will be reviewed with potential study subjects by a qualified member of the study team. The informed consent process will follow applicable institutional and regulatory guidelines. Subjects will be provided adequate time to review the informed consent document and all questions will be answered to the satisfaction of the subject prior to signing the informed consent.

If the subject is willing to participate in the clinical study, he/she or an authorized legal representative must sign the informed consent form indicating that they have read and understand the information provided. Each site will follow their local Institutional Review Board (IRB) and applicable regulatory guidelines for obtaining informed consent. Documentation of the informed consent process for each subject and the original signed informed consent will be retained at the site and as required by applicable regulations. A copy of the signed informed consent will be provided to the subject.

## 6.2.2 Preoperative Eligibility

Once written informed consent has been obtained, the Preoperative CRF will be completed to document adherence to the preoperative inclusion and exclusion criteria.

Where a subject fails to fulfill any element of the preoperative eligibility criteria, this will be documented and any signed consent form and completed preoperative inclusion/exclusion criteria retained. This information will be tracked on the Screening and Enrollment Log. The subject will not be advanced any further into the clinical study.

## 6.2.3 Subject Identification

After a subject has signed informed consent and met the preoperative inclusion and exclusion criteria, the subject will be allocated to the next available study number (subject ID number), which will be assigned.

The subject ID number will consist of the site number and the subject number. The subject number will be 01 for the first subject, 02 for the second subject and so on. This subject ID number will be the unique identifier of the subject and included on each CRF page and all other study-specific documentation relating to that subject.

## 6.3 **Preoperative Procedures and Evaluations**

The following data will be collected and recorded at the preoperative visit on the Preoperative CRF:

- Demographic data
  - o Age
  - Gender
  - Race and ethnicity
- Physical exam
  - Height
  - Weight
- Medical history
  - Disease process(es) / indication(s) for surgery
  - Concomitant illnesses
  - Preoperative anticoagulation and antiplatelet regimen, if applicable

## 6.4 Intraoperative Procedures and Evaluations

All subjects will undergo the same intraoperative study evaluations. Intraoperative is defined as the time interval from when the subject enters the surgical suite until the subject exits the surgical suite.

Subjects undergoing the non-emergent cardiothoracic surgeries are eligible for enrollment into the clinical study. The Investigator will perform the surgery per his or her standard procedures, including conventional methods of hemostasis where practical (pressure, ligature, cautery, etc.).

Both test and control devices (not opened or prepared) should be available at the start of each procedure.

## 6.4.1 Intraoperative Inclusion Criteria

A subject must then meet all of the following intraoperative inclusion criteria:

- Subject does not have an active or suspected infection at the surgical site;
- Subject in whom the Investigator is able to identify a TBS for which any applicable conventional means for hemostasis are ineffective or impractical; and
- Subject has a TBS with minimal, mild, or moderate bleeding.1

If all of these intraoperative eligibility criteria are met, then the subject is formally enrolled into the clinical study and randomized. Each subject will have one TBS assessed and documented for the purposes of this study.

The bleeding severity of the TBS will be assessed via the SBSS/SPOT GRADETM for intraoperative inclusion, which is immediately prior to enrollment. The bleeding severity of the TBS will also be assessed and confirmed immediately prior to hemostat application, as bleeding severity may change between the time of enrollment and when the hemostat is ready to be applied. Both bleeding severities will be recorded on the Intraoperative CRF. Both bleeding severities will be presented in the analysis of the study data.

If the bleeding severity at the time when the hemostat is ready to be applied is not minimal, mild, or moderate bleeding, then the TBS will not be treated. If another suitable TBS is identified, the subject may undergo intraoperative evaluations for that TBS. If another suitable TBS is not identified, the subject will be withdrawn from the clinical study.

## 6.4.2 Randomization and Hemostat Application

Subjects will be randomized to receive HEMOBLAST™ or FLOSEAL in a 1:1 ratio:

- 52 subjects will be randomized to receive HEMOBLASTTM; and
- 52 subjects will be randomized to receive FLOSEAL.

To ensure balance through time, blocked randomization will be performed. Random block sizes of 2, 4, or 6 will be implemented to conceal treatment allocation. After enrollment and randomization, the assigned hemostat will be used in the subject.

A study-specific stopwatch will be used in the performance evaluations.

After randomization, the assigned hemostat will be opened and prepared. The study-specific stopwatch will be started at the time of hemostat outer packaging opening (time 00:00).

The assigned hemostat will be prepared and applied to the TBS per its respective Instructions for Use (IFU).

At time 03:00 (3 minutes after hemostat packaging opening), hemostasis will be assessed using the SPOT GRADETM. If the TBS is hemostatic (SPOT GRADETM score = 0), the performance evaluations are complete. If the TBS is not hemostatic (SPOT GRADETM score > 0), a re-application of the assigned hemostat will be performed per the respective IFU.

At time 05:00 (5 minutes after hemostat packaging opening), hemostasis will be assessed using the SPOT GRADETM. If the TBS is not hemostatic (SPOT GRADETM score > 0), the Investigator may use any means necessary to obtain hemostasis.

The study-specific stopwatch will run continuously until the 5 minute evaluation time point, except in cases where preparation of the hemostat is interrupted by other activities and obligations of the surgical staff. The study-specific stopwatch will be run by a trained and delegated study staff member. In cases where the individual(s) involved in preparing the hemostat are required to perform other activities, the stopwatch will be paused and restarted when preparation resumes. The number of interruptions will be recorded for each case.

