## 8.4 Training

Principal Investigators and study site staff will be trained on the clinical study and the specific tasks to which they are delegated. Study site staff will also have documented training on Good Clinical Practice.

Further, Investigators (Principal Investigators and sub-investigators responsible for enrolling study subjects and applying the hemostatic devices) will have training on use of the test device, control device, and the SPOT GRADETM.

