## 11.3.1.2 Methods of Analysis

The primary efficacy endpoint is the difference in the probability of TTH at 3 minutes comparing HEMOBLASTTM to FLOSEAL. Letting  $\theta$  denote the true difference in the probability of hemostasis at 3 minutes between HEMOBLASTTM to FLOSEAL, the trial will test the null hypothesis H0:  $\theta \le 0$  vs. the alternative hypothesis HA:  $\theta > 0$  using a one-sided level 0.025 Wald test. The resulting p-value based upon the asymptotic normal distribution and a corresponding (2-sided) 95% confidence interval for the difference in binomial proportions (HEMOBLASTTM minus FLOSEAL) will also be computed and reported.

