## 15.2 Clinical Study Personnel Responsibilities

Prior to the initiation of this clinical study, each Principal Investigator will approve this Protocol by signing the signature page. This signature confirms that the clinical study will be performed in compliance with the Protocol.

The Sponsor shall also provide accurate, complete, and current information about any aspect of the clinical study as requested by reviewing IRB(s) or regulatory authorities. Current applicable national regulations shall be followed.

The Sponsor is also responsible for the retention of clinical study documentation per applicable regulations.

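### The block sizes meant to conceal allocation are printed in the protocol that each Principal Investigator signs, while the list structure and the release of assignments are not stated

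*Combined protocol and SAP*

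**What the plan says.** Section 6.4.2 of the protocol sets 1:1 blocked randomization and states: "Random block sizes of 2, 4, or 6 will be implemented to conceal treatment allocation". Section 15.2 requires that "each Principal Investigator will approve this Protocol by signing the signature page", so the sizes reach every Principal Investigator. Section 8.4 describes the users of the devices as "Principal Investigators and sub-investigators responsible for enrolling study subjects and applying the hemostatic devices", so the signatories are among those who enroll.

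The target bleeding site (TBS) is chosen by the Investigator. The criterion in section 6.4.1 begins "Subject in whom the Investigator is able to identify a TBS for which any applicable conventional means", and once the intraoperative criteria are met, "then the subject is formally enrolled into the clinical study and randomized". Table 7 gives the order as identify the TBS, grade it, randomize. No blinding is described, and section 6.4.2 says: "After randomization, the assigned hemostat will be opened and prepared". Past assignments at a site are therefore known to the surgical team.

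The protocol does not say whether there is one central list or one list per site. It names no mechanism, such as sealed envelopes or a web or telephone system, that holds back an assignment until it is due.

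**The concern.** Varying block sizes protect most when the people who enroll do not know them. Here the sizes are the only concealment measure stated, and the document that relies on them also gives them away. The smallest size is 2.

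The opportunity comes before randomization. The Investigator decides which bleeding site becomes the TBS, within eligible grades from minimal to moderate and with a judgment about whether conventional means will do. Someone who expects a particular arm next could, without intending to, settle on an easier or a harder site. That would make the arms differ at baseline in a way that analysis can only partly repair, and the 3-minute proportion that defines study success would carry the difference.

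**Working it through.** **Inputs**
- Sizes 2, 4 and 6, ratio 1:1 (section 6.4.2). Their probabilities are not given; equal thirds are assumed.
- Up to 104 subjects over up to 5 sites, with "approximately 20 subjects will be enrolled per site, with no more than 50% of the subjects being enrolled at any single site" (section 2.4.2). Since 104/5 = 20.8, site lists of 20 are used.
- List structure is not stated, so both cases are computed.
- The effect of TBS choice on success, x = 5 points either way, is an assumption. The documents give no figure.

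The plan states no predictability figure to reproduce. Its sample size does reproduce: comparing 0.40 with 0.10 at one-sided 0.025 and 90% power, with continuity correction, gives 49 per arm, or 98. Then 98/0.95 = 103.2, rounded up to 104. Nothing below changes it.

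**Step 1. Guess rate from small blocks.** Someone who names the arm that is behind, and tosses a coin when the arms are level, gets on average b/2 + ½(2^b / C(b, b/2) − 1) right in a block of size b.
- b = 2: 1 + ½(4/2 − 1) = 1.50 of 2, or 75.0%
- b = 4: 2 + ½(16/6 − 1) = 2.83 of 4, or 70.8%
- b = 6: 3 + ½(64/20 − 1) = 4.10 of 6, or 68.3%
- Equal mix: (1.50 + 2.83 + 4.10)/12 = 70.3%, against 50% with no information

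**Step 2. What knowing the sizes adds.** In simulated 20-subject site lists, a guesser who knows the sizes and computes the exact probability of each next arm is right 69.7% of the time. A guesser who knows nothing about the sizes and follows the running imbalance is also right 69.7% of the time. The reason is structural. Every block ends level, so when one arm is ahead, the unfinished block holds more of the other. When the arms are level, neither is favored. The sizes change confidence in the guess, not its direction.

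Knowing the sizes does create certainty. For example, a lead of three can arise only in a block of 6, so the next three assignments are settled. About 3.7% of allocations are certain, and about 27% of site lists contain at least one. For someone who knows the sizes, 59% are predictable with probability 0.75 or more.

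**Step 3. One central list.** If all sites draw from one list of 104 and each investigator sees only their own site, the running-imbalance guess is right 51.6% of the time at a site with 20% of subjects and 53.4% at a site at the 50% cap.

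**Step 4. Bias.** If the success probability moves by x toward the expected arm, the difference between arms is biased by 2x(2g − 1), where g is the guess rate.

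| List | g | Bias at x = 5 points |
|---|---|---|
| Per site, sizes 2/4/6 | 0.697 | 2 × 5 × 0.394 = 3.9 |
| Per site, sizes 4/6/8 | 0.671 | 2 × 5 × 0.342 = 3.4 |
| Central, site with 20% | 0.516 | 2 × 5 × 0.032 = 0.3 |
| Central, site with 50% | 0.534 | 2 × 5 × 0.068 = 0.7 |

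For scale, at the upper end (site lists, common true rate 0.25, x = 5 points), simulation puts the type I error of the "one-sided level 0.025 Wald test" at about 0.067.

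**Step 5. Other mixes, on 20-subject site lists, if the sizes became known**

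| Sizes | Guessed | Probability 0.75 or more | Certain |
|---|---|---|---|
| 2/4/6 | 69.7% | 59% | 3.7% |
| 4/6 | 68.5% | 46% | 6.0% |
| 4/6/8 | 67% | 37% | 2.5% |

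Dropping size 2 without adding a larger size raises the share of certain allocations.

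**The case against.** The strongest objection concerns cause. A reader might infer that printing the sizes produces the 70% guess rate and the bias of about 4 points. It does not. Step 2 gives the same rate with the sizes unknown, so deleting the sentence alone would leave that bias in place. What disclosure adds is the certain guesses, and mixing the sizes already keeps these few: a fixed size of 2 would make 50% certain. Nor is a guess at probability 0.75 close to certain.

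Second, the upper figures need site-level lists. Section 6.4.2 mentions no stratification by site, gives balance through time as its aim, and fixes 52 per arm. All of that fits a central list at least as well, and there the bias falls to well under 1 point. This stands, and it is why a range is given.

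Third, the plan already limits the room for selection. Eligibility bounds the choice of TBS, Table 7 puts identification and grading before randomization, and the time of randomization is recorded. Location, dimensions and baseline grade are also recorded, and results are shown by severity, so some differential selection would be visible. This stands too. What is missing is anything that makes the order binding.

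The objection limits the size of the problem. It does not explain why the sizes should be printed where concealment is their stated purpose.

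**Conclusion.** The point holds in a limited form. The plan names one concealment measure and discloses it to the people who enroll. Disclosure itself costs little: about 3.7% of allocations become certain under site lists. The wider exposure comes from small blocks with visible past assignments, and its size depends on a list structure that the protocol leaves open. Under the assumed 5-point shift, the bias lies between about 0.3 and 4 points. That range also rests on equally likely sizes, site lists of about 20, and investigators who follow earlier assignments.

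A reader might also infer that the same unblinded investigator who picks the TBS scores the outcome. The documents do not establish this. They name no assessor for the 3- and 5-minute scores; section 8.4 says only that Investigators are trained on the scale. The absence of blinding is likewise a reading of what is described, since the protocol never calls the trial open-label. The change is worth making because it costs almost nothing, not because a large bias has been shown.

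**What to change.** 1. In section 6.4.2, replace the sentence on sizes with wording such as *randomly varying block sizes held in a restricted randomization document*.
2. In that document, drop size 2 in favor of a larger mix such as 4, 6 and 8. On site lists, if these became known, about 67% would be guessed, 37% at probability 0.75 or more, and 2.5% certain.
3. Release each allocation only after the TBS and its SPOT GRADE have been entered. This makes the order in Table 7 binding. It prevents changes to the entered choice or grade once the arm is known, but does not stop a guess beforehand. It also does not cover the replacement TBS that section 6.4.1 allows after randomization, which is a separate matter.
4. Settle whether the list is central or per site and record it with the sizes, since this decides which end of the range applies.

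The cost is one protocol sentence, a regenerated list and a release step. The statistical downside is a possible imbalance of a few subjects from unfinished blocks, one per list: at most half a block each, so four subjects with size 8 against three with size 6. Sample size and alpha do not change.
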